- 2) Seasonal Newsletters providing updates about study progress on recruitment, patient testimonies about their experiences with clinical research, NNHSC clinic updates from [name], health tips and information, and seasonal activities that support healthy lifestyles. The purpose of the newsletters is to keep participants engaged with the study in between their telephone interviews, thereby increasing retention and minimizing attrition.
- 3) Small participant incentive items using the same graphics and messaging from the general clinic campaign will be mailed with the reminder letters (e.g., water bottles, draw string bags, small ear buds, T-shirts). Consistently using the same images and themes across recruitment and retention materials will generate familiarity with the study and will serve to maintain high retention rates.

All recruitment and retention materials will be mailed from NNHSC.

Randomization and Study Conditions

Smokers identified through the SQL query from NNHSC's EHR and who consent to enroll in the NNHSC "health habits and wellness service needs study" and who complete the baseline survey will be randomized to either **Usual Care** or person-centered population management (**Choose to Change**) four weeks (week 0) after enrollment in the study (week -4). We will use a 6:6 permuted block randomization scheme to assign patients to treatment condition. Randomization will be stratified by readiness to quit, as measured using a single item question for which participants identify their level of motivation to quit smoking as measured on a 10-point scale (1 = not at all motivated; 10 =extremely motivated), race (African American versus not), and language preferred (English versus Spanish). We plan to approach 115 patients per month to enroll 40 participants per month and achieve this randomization rate (35% response rate).

Choose to Change (CtC) Intervention: Choose to Change will comprise two components: 1) a single page letter that messages choice of cessation or smoking reduction using words and a graphic; and 2) five automated text messages sent on behalf of the NNHSC providers that reinforce the central messaging of the letter.

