PROTOCOL SHORT TITLE: Choose to Change – Reducing Tobacco Disparities

[figure not shown]
outcomes.⁹⁹ Text messaging improves attendance at healthcare visits,^{100,101} adherence to diabetes self-care¹⁰² and weight management regimens,¹⁰³ as well as the effectiveness of smoking cessation treatment.⁹⁹ Popularity of text messaging is high across racial/ethnic groups, socioeconomic levels, and ages.¹⁰²

Two weeks after letter mailing, participants will be contacted by a Quitline counselor and offered free person-centered behavior counseling (cessation or reduction-focused depending upon patient preference) and free NRT (patch, gum, or lozenge) if determined as safe and appropriate. Please see more detail regarding the proactive Quitline treatment below.

Usual Care Condition: Participants assigned to this clinic-based control comparison will receive NNHSC clinic-based care for smoking that follows the Ask, Advise, Refer approach.¹⁹ Following the practice adopted by NNHSC in 2011, a Usual Care participant who smokes will receive a referral for proactive Quitline treatment according to the following established clinic procedure: If the participant is seen in the clinic for a health problem or routine evaluation, a medical assistant will confirm current smoking and advise the participant to quit using clear and strong language. Current smoking and advice to quit are documented in the EHR system and the participant will be seen by the provider who addresses the purpose of the visit. If the provider also addresses the participant's smoking, establishes that the participant is motivated to set a quit date, and the participant agrees to the Quitline referral, a referral form is generated via the EHR system. Referrals are transmitted electronically via the Quitline website by the Care Coordinator. Participants who are referred will receive a call from the Quitline within 48 hours. Usual Care participants who accept Quitline treatment will receive free person-centered smoking cessation counseling and free NRT (patch, gum, or lozenge). Please note: providers may still refer patients who are not enrolled in this study to the Quitline.

In both conditions, Quitline treatment will continue as accepted or initiated by participants over 28 weeks.

Figure 3. Choose to Change Intervention Workflow

Choose to Change Intervention Clinic Workflow

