All outcomes of interest for **Primary Aims 1-3** are binary (treatment engagement, treatment utilization, smoking cessation) and can be analyzed using logistic regression methods. Analyses will be conducted first using an ITT principle (missing=treatment failures). We will also conduct an adherence sample analysis that includes only participants reached at the 28-week follow-up ($\geq 75\%$ of the sample based on our experience). This approach addresses the question of effectiveness more directly, but it is subject to more bias if attrition is large or differential by treatment condition. Therefore, we will complement it by analysis of non-response patterns using sociodemographic (age, gender, race, ethnicity, marital status, household income, education), and healthcare (time since last clinic visit, type of health insurance) characteristics. These can be used to create propensity scores that allow for inverse-probability-weighting (IPW) of observed outcomes^{116,117} to achieve balance across potential confounders of the treatment-to-outcome relationship. Ideally, the distribution of propensity scores will show large overlap across study conditions. If not, that will be taken as evidence that completers are not comparable on measured confounders across conditions, and that one should refrain from

PROTOCOL SHORT TITLE: Choose to Change – Reducing Tobacco Disparities

further comparisons. PROC GENMOD of SAS/STAT 9.2¹¹⁸ can handle subject-level probability weights. Similar findings across all three approaches would increase confidence in the results overall. Both raw and adjusted rates will be presented for each outcome by study condition. For the cessation outcome, we will also explore the impact of smoking history (e.g., past year quit attempts, past referral for Quitline treatment), race, and gender on non-response. We will also use propensity score modeling to examine the relationship between treatment utilization at 14 weeks and abstinence at 28 weeks. Since available data indicate little effect of NRT type on outcome, we will model NRT dose/duration, while controlling for patterns of utilization.

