Exploratory Aim 1 (Moderators of Choose to Change Effects). We will focus our search for moderators on baseline variables such as readiness to quit, health literacy,⁷¹ smoking level, time since the patient's last clinic visit in which smoking was addressed, and recent smoking reduction.⁵³ Participants who smoke more than 10 cigarettes per day, who have recently attempted to reduce their smoking, and those lower on motivational readiness to quit are expected to be disproportionately responsive to Choose to Change intervention. In addition, participants with lower literacy and those with a more recent clinic visit during which smoking was addressed are expected to be especially likely to benefit. These factors are expected to be especially responsive to the person-centered and the low-income targeted elements of the Choose to Change intervention (Figure 2), though we realize that there may be other potential moderators. Other variables to be explored as potential moderators include initial choice of smoking cessation versus reduction, and race/ethnicity. Analysis will be conducted using logistic regression, with a separate model for each outcome variable. The predictor variables will include treatment condition, the moderator variables, and their two-way interactions with condition. Sociodemographic (e.g., gender), psychosocial (e.g., perceived stress), and smoking (e.g., menthol cigarette use) variables known to influence smoking cessation will serve as covariates.

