i.e., no more than minimal risk to participants. Second, informed consent cannot be obtained without seriously threatening the validity of the study. The focus of this study is to evaluate the extent to which the Choose to Change letter motivates patients to engage in and use Quitline treatment to achieve short-term smoking cessation. The Choose to Change intervention is novel in that it attempts to increase engagement in treatment through encouraging a variety of initial treatment goals, ranging from abrupt smoking cessation to gradual smoking reduction to simply learning about smoking and smoking cessation. The central idea is that smokers who are highly ambivalent about quitting will be more motivated to engage in Quitline treatment because there will be no pressure to set a quit date and abruptly quit. The usual approach to smoking cessation treatment in primary care requires a commitment to abrupt quitting. Disclosure of this flexible approach to addressing smoking cessation would expose Usual Care participants to the central message of the Choose to Change intervention and significantly undermine our ability to observe an intervention effect on Quitline engagement, utilization, and cessation. Disclosure of Quitline treatment would result in a small sample of participants who are ready to quit smoking, significantly undermining our intent to address smoking among patients who are not ready to attempt quitting (95% of all smokers). As achieved in our past randomized controlled trials,¹⁸⁻²⁰ a waiver of informed consent allows for the entire population of eligible smokers to be included in the study, thereby achieving a true assessment of the effectiveness of Choose to Change versus Usual Care without selection bias. Third, the waiver will not adversely affect the rights and welfare of participants. Patients randomized to the Choose to Change arm are given multiple opportunities to opt themselves out of the Choose to Change text messages and referral to the Quitline. After the final survey has been completed, Usual Care participants who report continued smoking will be offered a referral to the Quitline.

Debriefing

Once the study is complete and all participants have completed their last follow-up survey, all participants will be fully debriefed via newsletter (emailed or traditionally mailed, based on participant preference) regarding the randomized controlled trial.

Process to Document Consent in Writing

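### Moderation is specified only on the odds-ratio scale while Usual Care referral depends on motivation to quit, so the conclusion about low-readiness smokers may depend on the scale

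*Combined protocol and SAP*

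**What the plan says.** - **Moderator model** (Statistical Analysis Plan, Exploratory Aim 1): "Analysis will be conducted using logistic regression, with a separate model for each outcome variable". On what enters each of these models, the plan states: "The predictor variables will include treatment condition, the moderator variables, and their two-way interactions with condition". No contrast of risk differences and no rates by moderator level are named.
- **Directional prediction** (same paragraph): "those lower on motivational readiness to quit are expected to be disproportionately responsive to Choose to Change intervention". The scale on which responsiveness is judged is not given.
- **Rates to be reported** (Data Analysis): "Both raw and adjusted rates will be presented for each outcome by study condition". Rates within moderator levels are not promised.
- **Usual Care pathway** (Randomization and Study Conditions): a clinic referral is generated if the provider addresses smoking, "establishes that the participant is motivated to set a quit date, and the participant agrees to the Quitline referral". The Incomplete Disclosure section makes the same contrast: "The usual approach to smoking cessation treatment in primary care requires a commitment to abrupt quitting".
- **Choose to Change pathway**: participants are called by the Quitline two weeks after the letter unless they opt out, whatever their readiness.
- **Route open in both arms**: "Quitline treatment will continue as accepted or initiated by participants over 28 weeks".
- **Readiness**: a single 10-point item, used as a stratification factor: "Randomization will be stratified by readiness to quit".

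**The concern.** In logistic regression, a condition-by-moderator term is the log of a ratio of two odds ratios. When control rates differ between groups, that ratio and the difference in risk differences are different quantities. They can differ in size, in significance and in sign.

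Here there is a specific reason to expect different control rates. The Usual Care referral route runs through a judgement about motivation to set a quit date, which is close to the moderator. If few low-readiness Usual Care participants reach the Quitline, even a modest absolute gain becomes a large odds ratio. The plan predicts a direction for exactly this moderator, and reaching smokers not ready to quit is central to the trial's rationale. A significant interaction could therefore be reported as low-readiness smokers gaining more when the extra number engaged per 100 is the same in both groups, or smaller in theirs.

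**Working it through.** **1. The plan's own figures.** Power section and Table 3: 265 per arm, two-sided alpha 0.05, engagement 10% v 24%. The pooled normal approximation without continuity correction is

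power = Φ{[|p2 − p1| − 1.96·√(2·p̄(1 − p̄)/n)] / √[(p1(1 − p1) + p2(1 − p2))/n]}.

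For Aim 1, p̄ = 0.17, so power = Φ[(0.14 − 1.96 × 0.0326)/0.0321] = 99.1%, against 99% stated. Aim 2 (7% v 15%) gives 83.9% against 84%, and Aim 3 (2% v 7%) gives 79.5% against 80%. The stated powers reproduce. No figure is given for the moderator analysis.

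**2. Assumptions not in the documents.** Readiness is split into low and high halves, so 265/2 ≈ 132 per arm per level. Rates by level are free, but must average to the plan's 10% and 24%.

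**3. Equal absolute gain.** Each level gains 14 points. OR = [c/(1 − c)]/[u/(1 − u)], where u is the Usual Care rate and c the Choose to Change rate. For Usual Care 2% low and 18% high:

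- low: (0.16/0.84)/(0.02/0.98) = 9.33
- high: (0.32/0.68)/(0.18/0.82) = 2.14

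Each scenario was simulated 200,000 times. The logistic interaction was a two-sided 5% Wald test of ln(OR low/OR high), with trials lacking a finite estimate counted as non-significant. The additive contrast was a z-test of RD low − RD high.

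| Usual Care low/high | Choose to Change low/high | OR low v high | Logistic test: low more responsive | RD test rejects (either direction) |
|---|---|---|---|---|
| 2% / 18% | 16% / 32% | 9.33 v 2.14 | 47% | about 5% |
| 3% / 17% | 17% / 31% | 6.62 v 2.19 | 38% | about 5% |
| 5% / 15% | 19% / 29% | 4.46 v 2.31 | 20% | about 5% |
| 8% / 12% | 22% / 26% | 3.24 v 2.58 | 6% | about 5% |

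In the first row about 7% of trials have no finite estimate. An analytic Wald approximation for that row gives 53%; the simulated figure is lower partly because those trials count as non-significant.

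**4. Smaller absolute gain in low readiness.** Usual Care 2%/18%, Choose to Change 12%/36%: gains of 10 v 18 points, OR 6.68 v 2.56. The logistic test significantly favours low readiness in 12% of trials; the RD test significantly favours high readiness in 26%.

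**5. Where the odds-ratio contrast vanishes or changes sign.** Keep Usual Care at 2%/18% and the Choose to Change average at 24%:

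- Choose to Change 6.2%/41.8%: the odds ratios are equal at about 3.3, with gains of 4.2 v 23.8 points.
- Choose to Change 5%/43%: OR 2.58 v 3.44, now larger in high readiness.
- Choose to Change 24%/24%: OR 15.5 v 1.44 and gains of 22 v 6 points, so both scales favour low readiness.

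**The case against.** The strongest reply is that a logistic interaction is a standard choice for a binary outcome, and that the percentages in the equal-gain table count as misleading only if equally responsive means equal risk difference. Start instead from equal odds ratios (Usual Care 2%/18%, Choose to Change 6.2%/41.8%) and the RD test declares high readiness more responsive in 90% of trials, while the logistic test favours either group in only about 3%. Neither scale is wrong; they answer different questions. The aims are worded as proportions, but that does not settle the matter, since the Power section supports Aim 2 with an odds ratio. This stands. It is a reason to report both scales rather than replace one with the other.

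A reader might also infer that a larger odds ratio in low-readiness smokers is guaranteed by the design. The documents do not support that. The contrast depends on Choose to Change engagement by readiness, which is nowhere given; if the letter and calls did nothing in that group, 2% v 2% would give an odds ratio of 1. Nor do the documents show that Usual Care engagement is near zero there. The referral condition is a provider's judgement at a clinic visit, not the baseline 10-point item, and participants can start Quitline treatment themselves.

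Finally, a larger effect in low-readiness smokers need not be an artefact of the comparator. Bypassing the quit-date requirement is part of what the trial evaluates, and the gain may be larger on both scales. The even split used here is also simpler than the plan's model, which has several moderators and covariates and sets no cut-point.

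**Conclusion.** The concern holds in a limited form. The plan predicts greater responsiveness in low-readiness smokers, tests it on the odds-ratio scale alone, promises no rates by readiness, and uses a comparator whose referral route probably lowers engagement in that group. The planned analysis can therefore support a claim that the absolute rates do not.

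How often depends on unknown Usual Care rates: under an equal 14-point gain, from 47% of trials at a 2%/18% split down to 6% at 8%/12%. The stronger misreading, a significant result for low readiness when its absolute gain is smaller, occurred in 12% of trials in the one such case simulated. All these figures rest on the assumed even split and assumed rates by readiness.

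The referral condition acts directly on engagement and utilization and only indirectly on cessation. The aim is exploratory, no rule for interpreting it is written, and Primary Aims 1 to 3 are unaffected. This is a cheap improvement, not a fault that threatens the trial.

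**What to change.** In Exploratory Aim 1 of the Statistical Analysis Plan, for engagement and utilization:

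- Prespecify arm-specific rates and risk differences by readiness level, stating how the 10-point item will be grouped or at which values predictions will be made.
- Prespecify the difference in risk differences with a confidence interval, either from the same logistic model with bootstrap intervals or from a linear model with robust standard errors.
- Keep the odds-ratio interaction and report it beside these.
- State that no claim of greater responsiveness will rest on the odds ratio alone, and that if the scales disagree the result will be reported as scale-dependent.

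The cost is a paragraph of plan text and a few lines of code, with no new data. The downside is that two scales are reported and may disagree, which makes the result harder to summarise.

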PROTOCOL SHORT TITLE: Choose to Change – Reducing Tobacco Disparities

Protocol Title: **Reducing Tobacco Use Disparities Among Adults in Safety Net Community Health Centers**

Principal Investigators: [name]. (Lead PI)
Northwestern University
[contact]
[contact]

[name]. (Co-PI)
University of Illinois at Chicago
[contact]

[name]. (Co-PI)
Northeastern Illinois University
[contact]

[name]. (Site PI)
Near North Health Services Corporation
[contact]

[name]. (Site PI)
Alliance of Chicago

Biostatistician: [name].
Brown University
[contact]

Version Date: May 14, 2018

ClinicalTrials.gov
Registration Number: NCT03077737

PURPOSE OF STUDY & OBJECTIVES

An estimated 26 million smokers still receive no treatment for their smoking during their primary care visits. Given the persistent clinical system, provider, and patient barriers to addressing smoking, especially among poor populations, an EHR-automated population health management approach that links a healthcare system with community services both clinically and electronically to engage all smokers may increase access to effective treatment. Increased access is especially significant for low-income smokers who are underserved and carry a disproportionate burden of tobacco-related disease. This 2-group randomized controlled trial will evaluate the effectiveness of a person-centered population health management intervention for smoking cessation in low-income smokers. The following aims and hypotheses will be tested:

Primary Aim 1 (Effect on Treatment Engagement): Compare Choose to Change versus Usual Care for engaging low-income smokers in treatment. Hypothesis: Choose to Change will increase the proportion of smokers who complete a behavior counseling call by 6 weeks (24%), compared with Usual Care (10%).

Primary Aim 2 (Effect on Treatment Utilization): Compare Choose to Change versus Usual Care for increasing treatment utilization. Hypothesis: Choose to Change will increase the proportion of smokers who complete ≥ 1 additional behavior counseling calls by 14 weeks (15%), compared with Usual Care (7%).

Primary Aim 3 (Effect on Smoking Cessation): Compare Choose to Change versus Usual Care for increasing smoking cessation. Hypothesis: Choose to Change will increase the proportion of smokers

PROTOCOL SHORT TITLE: Choose to Change – Reducing Tobacco Disparities

abstinent at 28 weeks (7%), as defined by bio-verified 7-day point-prevalence abstinence, compared with Usual Care (2%).

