PROTOCOL SHORT TITLE: Choose to Change – Reducing Tobacco Disparities

- 8) Sending seasonal newsletters about living a healthy lifestyle;
- 9) Demonstrating a positive and caring attitude towards participants¹⁰⁹;
- 10) Rapid rescheduling of missed appointments; and
- 11) Acknowledgement and appreciation of participant effort.

These enrollment and retention strategies have been effective in pragmatic clinical trials and community studies of underserved populations,¹¹²⁻¹¹⁵ as well as in our ongoing cohort study (N01 HC48049).

STATISTICAL ANALYSIS PLAN

Power

To address power for hypotheses related to **Aim 1 (Treatment Engagement at 6 Weeks)**, we base our estimates for the proportion of participants completing a Quitline session by 6 weeks in the Choose to Change condition on our pilot study that resulted in a **24%** engagement rate. As for the Usual Care condition, we expect that current NNHSC Ask, Advise, Refer practice involving the Quitline as the primary referral program will result in a tripling to **10%** of the 3.3% engagement rate achieved in our EHR fax-referral project, in which our NIH-funded study of long-term nicotine patch treatment, with inclusion and exclusion criteria, served as the primary referral program.⁹⁴ Assumed rates by condition for each of the three outcomes of interest and participants per condition are presented in Table 3. We propose that a minimum of N=265 independent participants be randomized to Choose to Change versus N=265 to Usual Care, for a total N=530. Such a 1:1 allocation ratio guarantees **99% power** for the comparison of Choose to Change versus Usual Care at two-sided alpha=.05. This sample size requirement equates to 40 participants per month over the 15-month randomization period. In our three-week pilot study, 132 patients were processed through the workflow in Figure 3, a rate of 175 per month.

Table 3. Assumed Intent-to-Treat Rates by Condition for the Three Outcomes of Interest and Participants per Condition

Study Aim	Usual Care	Choose to Change
Aim 1: Engagement (6 Weeks)	10%	24%
Aim 2: Utilization (12 Weeks)	7%	15%
Aim 3: Cessation (26 Weeks)	2%	7%
Participants	265	265

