Our power estimates for **Aim 2 (Treatment Utilization at 14 Weeks)** will be based on Williams et al.⁹ who reported a 30% utilization rate for combined counseling and medication at a later time point than ours (6 months), following a face-to-face SDT-based intervention. Assuming 6-month utilization rates (one or more counseling calls after the initial counseling call) for the Usual Care and Choose to Change conditions of **7%** and **15%**, respectively, would be consistent with their treatment utilization odds ratio of 2.38 (95% CI=1.67-3.39), albeit at a lower baseline rate than they report. Our proposed randomization plan guarantees **84% power** for the comparison of Usual Care versus Choose to Change at two-sided alpha=.05.

Our power estimates for **Aim 3 (Smoking Cessation at 28 Weeks)** will be based primarily on Rigotti et al.²⁷ who reported 7-day point-prevalence abstinence rates at 14 weeks of 1% for standard care and 5% for population mail outreach under an Intent-to-Treat (ITT) approach. We expect that these 12-week ITT rates will rise to 3% in our Usual Care condition and 10% in the Choose to Change condition. Even if these rates then drop to **2%** in our Usual Care and **7%** in Choose to Change at 26 weeks, we still have **80% power** for the comparison of Choose to Change versus Usual Care at two-sided alpha=0.05.

Data Analysis

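### For cessation, the moderator model puts 16 to 21 parameters on at most about 24 expected quits, with no safeguard against sparse data

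*Combined protocol and SAP*

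**What the plan says.** Under Data Analysis, Exploratory Aim 1 assigns a separate logistic model to each outcome. On its content it says: "The predictor variables will include treatment condition, the moderator variables, and their two-way interactions with condition". Sociodemographic, psychosocial and smoking covariates are added, with one example of each kind. Read literally, this is one joint model holding every moderator and every interaction.

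That section names seven moderators: readiness, health literacy, smoking level, time since a visit that dealt with smoking, recent reduction, initial goal, and race/ethnicity. The list of aims at the front of the protocol adds primary language, making eight. The section also states the expected direction of effect for five of them.

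On size, the Power section asks for a minimum of "N=265 independent participants be randomized to Choose to Change versus N=265 to Usual Care, for a total N=530". Table 3 assumes cessation of 2% in Usual Care and 7% in Choose to Change. For that contrast the plan states that "we still have 80% power for the comparison of Choose to Change" over Usual Care. For the earlier time point it says: "We expect that these 12-week ITT rates will rise to 3% in our Usual Care condition and 10% in the Choose to Change condition".

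For the moderator model the plan gives no coding of the moderators, no penalised or exact method, no selection rule, no rule for a fit that does not converge, and no multiplicity rule.

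**The concern.** Because every moderator interacts with condition, each moderator slope in Usual Care is informed essentially by Usual Care quits alone. With seven moderators that means eight quantities (an intercept and seven slopes) resting on about five events. In data that thin, some combination of predictors often separates quitters from non-quitters perfectly, and an odds ratio then runs to zero or infinity.

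An analyst who follows the plan for cessation may therefore have to report unusable interaction estimates, or choose terms to drop or recode after seeing the data. The directional expectations could not be examined credibly for this outcome.

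**Working it through.** **1. Inputs.** 265 per arm; cessation 2% and 7% (Table 3); missing outcomes counted as failures (Data Analysis), so the rates apply to everyone randomized; two-sided alpha 0.05.

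**2. Reproducing the plan's figure.** Pooled normal approximation for two proportions:
- Mean rate 0.045; null SE = √(2 × 0.045 × 0.955 / 265) = 0.01801.
- Alternative SE = √((0.02 × 0.98 + 0.07 × 0.93) / 265) = 0.01788.
- z = (0.05 − 1.96 × 0.01801) / 0.01788 = 0.82, so power is 79.5%, against the stated 80%. The inputs are read correctly.

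**3. Expected quits.** 265 × 0.02 + 265 × 0.07 = 5.3 + 18.55 = 23.85. The probability of 8 or fewer Usual Care quits is 91%.

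This is a ceiling for 28-week quits, because the alternative study timeline ends follow-up at week 14 for those enrolled from February 2018. Their number is not given.

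**4. Parameters.** An intercept, condition, k moderators, k interactions and c covariates give 2 + 2k + c, with one term per moderator.
- k = 7: 16, or 19 with three covariates.
- k = 8: 18, or 21 with three covariates.
- Quits per parameter: 23.85 / 16 = 1.5 down to 23.85 / 21 = 1.1.

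**5. A separation check by hand.** Take a single binary moderator at 50% prevalence. A given level has no Usual Care quits with probability (1 − 0.5 × 0.02)^265 = 0.070. For either level this is 2 × 0.070 − 0.98^265 = 0.139 − 0.005 = 0.13. Simulation gave about 14%, so the problem exists even before moderators are combined.

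**6. Share of joint fits with no finite solution.** Simulated at 2%/7% and 265 per arm, with independent moderators and no true moderator effects. Coding and prevalence are assumptions.

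| Assumed coding (7 or 8 moderators) | No finite solution |
|---|---|
| All continuous | 2-5% |
| Mixed continuous and binary, no rare group | 27-40% |
| All binary, 50% prevalence | 39-44% |
| All binary, 30% prevalence | 67-72% |
| Mixed, plus a language term at 7% prevalence | 84% |

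Sensitivity to the number of quits:
- At the plan's 3%/10% rates, expected quits are 265 × 0.03 + 265 × 0.10 = 34.45. The share is 16% for seven mixed or 50:50 binary moderators, and runs from 0% to 69% across codings.
- If only 186 or 132 per arm had a 28-week outcome (assumed), it would be 65-69% or 78-85% for seven mixed or 50:50 binary moderators.

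**7. Fits that converge.**
- With mostly binary moderators the median interaction SE is about 1.02 on the log-odds scale. 80% power needs exp((1.96 + 0.84) × 1.02) = exp(2.86), a ratio of odds ratios near 17.
- For a true ratio of 3 (log 1.10), with seven 50:50 binary moderators, power is about 17% and the mean estimate 1.13, so there is little bias.
- With all-continuous moderators the SE is about 0.55 per SD, so exp(2.80 × 0.55) = 4.7 per SD.
- Under the null, each interaction test rejects in 2-5% of fits.

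**8. The other outcomes.** Engagement: 265 × (0.10 + 0.24) = 90 expected events. Utilization: 265 × (0.07 + 0.15) = 58.

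**The case against.** The strongest reply is that no single failure rate belongs to this plan. A reader might infer that about half of all such fits must fail. The documents do not support that: they fix neither coding nor prevalence, and readiness (a 10-point scale), cigarettes per day and time since last visit can all be entered as continuous. This stands, and it is why the result is given as a range. The all-continuous end is nevertheless unlikely, because initial goal and race/ethnicity are categorical and the plan itself describes smoking level by a cut at 10 cigarettes per day.

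A reader might also infer that sparse data produce false signals. They do not here. The chance of at least one nominally significant interaction across seven or eight is 15-32%. Independent 5% tests would give 1 − 0.95^7 = 30% and 1 − 0.95^8 = 34%. That is uncorrected multiplicity. The defect in the converged fits is imprecision.

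Finally, the aim is labelled exploratory, and its directional expectations are not specific to cessation. With about 90 and 58 expected events, the other two outcomes do not share the severity of the problem. That also stands, and it limits the point to one exploratory analysis. It does not justify a stated model that may have no finite solution.

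**Conclusion.** The point holds for the cessation moderator analysis only. The stated model has 16 to 21 parameters for at most about 24 expected 28-week quits, about 5 of them in Usual Care, and no provision for sparse data. These counts follow from the plan's own figures, assuming one term per moderator and three covariates at the upper end.

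Under mixed or 50:50 binary coding roughly 30-45% of fits have no finite maximum-likelihood solution. The share is a few percent if all moderators are continuous and about 84% with a rare language group. These percentages are conditional on assumed, independent covariate distributions and no true moderator effects. Converged fits with mostly binary moderators are too imprecise to detect anything but a ratio of odds ratios near 17.

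Nothing here bears on the primary analyses of Aims 1 to 3. It would also go too far to say that the moderator hypotheses cannot be examined at all, since engagement and utilization remain available.

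**What to change.** For cessation only, amend Exploratory Aim 1 as follows:

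- Replace ordinary maximum likelihood with Firth-penalised logistic regression and profile-likelihood intervals. This is the core of the change, because it keeps estimates finite. It is needed even for single-moderator models, given the separation rate of about 14%.
- Fit one moderator at a time: condition, the moderator, their interaction, and any stratification factor (readiness, race, language) that is not itself the moderator.
- Report every interaction with its interval, and present the cessation moderator results as descriptive.

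The change is to SAP wording alone. The downside is that moderators are not mutually adjusted and the further covariates in Exploratory Aim 1 drop out of the cessation model. Penalisation does not cure imprecision: with about five Usual Care quits the intervals will be wide under any model, hence the descriptive label. The engagement and utilization moderator models and the primary analyses stay as written.
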